2.10.2 Analysis of secondary efficacy variables

2.10.2.1 Secondary efficacy variables

Change from Baseline in derived gait speed (m/sec) at Week 24 and Week 48.

Change from Baseline in total SPPB score (including component scores: Total standing balance score, gait speed score and chair stand score) at Week 24 and Week 48.

2.10.2.2 Descriptive presentations

The same approach as specified for the primary efficacy variable in [Section 2.10.1.2](#) (Descriptive presentations) will be used for the presentation of the secondary efficacy variables (derived gait speed [m/sec] and total SPPB score), as well as the three component scores (total standing balance score, gait speed score and chair stand score). The actual time (sec) of the timed function tests (standing balance [sec], gait speed time [sec] and chair stand [sec]) and the total SPPB score category will also be presented. These aforementioned will be performed for all patients assigned to FAS at each windowed visit and change from Baseline at each windowed post-baseline visit and End of Treatment (derived)/End of Study (derived) as relevant. All summaries will be presented for each treatment group and “Active Total:

Efficacy”, overall and by the following [REDACTED] subgroups (except for the three component scores [total standing balance score, gait speed score and chair stand score] that will be summarized overall and not by each subgroup) as detailed in [Section 2.6](#) (Subgroups):

- Region (Japan/Non-Japan).
- [REDACTED]
- Fracture fixation type (internal [screws only, intramedullary {nails} and extramedullary fixation {plate, combinations}]/arthroplasty [hemiarthroplasty or total hip arthroplasty]).
- History of falls (yes/no [none]).
- Use of mobility aids prior to hip fracture (yes/no [none]).
- 25OH Vitamin D at Screening (< 30 nmol/L [<12 ng/mL] / ≥ 30 nmol/L [<12 ng/mL]).
- Amendment (pre-amendment 2/post-amendment 2).

In addition, the change from Baseline at Week 24 and Week 48 in total SPPB score category, will be presented as a shift table for each treatment group and “Active Total: Efficacy”. Percentages (%) will be derived relative to the number of FAS patients with a total SPPB score assessment available at Baseline/Randomization visit (Day 1) and at the relevant windowed visit.

2.10.2.3 Statistical model, hypothesis, and method of analysis (secondary)

The change from Baseline in derived gait speed (m/sec) and change from Baseline in total SPPB score at each windowed post-baseline visit will be analyzed using an MMRM in a similar manner to the primary efficacy variable (as specified in [Section 2.10.1.3](#) [Statistical model, hypothesis, and method of covariate analysis]). Treatment group, visit, region (Japan/Non-Japan), treatment date (early/late), fracture fixation type (internal [screws only, intramedullary {nails} and extramedullary fixation {plate, combinations}]/arthroplasty [hemiarthroplasty or total hip arthroplasty]), history of falls (yes/no [none]), use of mobility aids prior to hip fracture (yes/no [none]) and Baseline value will be included as covariates (see “Covariates” column of Table 2.2 [[Section 2.6](#) {Subgroups}]). In addition, the following six interaction terms will be fitted:

- Treatment group*visit.
- Region*visit.
- Treatment date*visit.
- Fracture fixation type*visit.
- History of falls*visit.
- Use of mobility aids prior to hip fracture*visit.
- Baseline value*visit.

An unstructured covariance matrix will be used for the Week 12 analyses, Week 24 analyses (primary analysis) and Week 48 analyses (final update analysis). The underlying assumptions of the mixed model (homogeneity of slopes and normality) will be assessed by the normality of the residuals within treatment groups. The homogeneity of the variance will be checked by Levene's test at the time of the primary analysis. If the variable is not normally distributed,

natural log transformation may be used (see [Section 3.11.1](#) [Mixed Model Repeated Measures {MMRM}]) for more details on how to assess normality). The antilog of the point estimate and associated 95% confidence interval of the treatment difference will be computed prior to presentation.

The following testing strategy will be used to control for multiplicity of endpoints and doses to be tested: if both doses (bimagrumab 700 mg and bimagrumab 210 mg) are statistically significantly different from placebo at $\alpha=0.05$ two-sided for the primary endpoint, then a fixed sequence approach will be applied for both derived gait speed (m/sec) and total SPPB score at Week 24 using the same linear mixed model for repeated measures and $\alpha = 0.05$ two-sided at each stage. The first inference will compare the bimagrumab 700 mg group to placebo for derived gait speed (m/sec), followed by a second inference comparing the bimagrumab 210mg group to placebo for derived gait speed (m/sec). The third inference will compare the bimagrumab 700mg group to placebo for total SPPB score, followed by a fourth inference comparing the bimagrumab 210mg group to placebo for total SPPB score. Additionally, the fifth inference will compare the combined bimagrumab 700mg and 210mg group to placebo for the incidence of falls observed until the time of the primary analysis. The sequence of the endpoints was decided based on the anticipated probability of showing statistical significance of bimagrumab over placebo, the clinical importance is not considered for this sequence determination, as each endpoint is clinically important.

The analysis conducted at Week 24 for falls (negative binomial) will include all available incidence of falls also collected from patients with visits beyond Week 24. The analysis of the fall data will be performed based on the assumption that the differences in incidences of fall within the active bimagrumab doses (700 mg and 210mg) are minimal compared to the differences with placebo.

No control will be used in comparing the change from Baseline at any visit (Week 12, Week 24 and Week 48) in secondary efficacy variables between the bimagrumab 70 mg dose and placebo.

(Secondary Objectives 1, 2 and 3)

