6.4.3 Gait Speed

Gait speed in this study will be assessed as part of the SPPB, over a 4 meter distance of a 6 meter course. Gait speed assesses a person's usual walking speed, which is defined as the speed a person normally walks from one place to another (e.g., walking from one store to another). The participant will perform two recorded trials of walking across the defined course. The fastest time in seconds (to the nearest 0.01 sec) a participant takes to complete the assessment will be scored and used to calculate the total SPPB score.

[figure not shown]
The patient should ideally complete the test without walking aids, unless he/she feels unsafe about completing the test without balance support (fears of fall). All types of walking aid(s) – except for wheeled walker / rollator – can be used during the treatment period (from Day 1 to EOS).

SPPB gait speed test performance will be captured in the eCRF including any potential usage of walking aids.

Details of the test are provided in the *Study manual*.

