Latham et al (2008)	Randomized, double-blinded, placebo-controlled trial	Patients >65 years undergoing surgical repair of a hip fracture	Gait speed at baseline 0.50 (0.28) m/sec. Gait speed at Week 12 0.77 (0.35) m/sec
Alley et al (2011)	Prospective study patients presenting for hip fracture repair	217 women > 65 y able to walk before hip fracture.	Gait speed at month 2 0.36 (0.17) m/Sec. Gait speed month 12 0.52 (0.24) m/Sec Standard deviation of gait speed change score ranging from 0.19 to 0.25 m/sec (*) in an analysis stratified for self-reported improvement perception outcome
Hardy et al (2007)	Prospective cohort study without intervention	439 community dwelling adults > 65 y. No use of assisted devices. Gait speed between 0.2 m/sec and 1.2 m/sec	Baseline Gait speed 0.88 (0.24) m/sec 1 year Gait speed 0.91 (0.29) m/sec Change scores 0.03 (0.19) m/sec

Based on the references above, in particular [Latham et al \(2008\)](#), it is anticipated that the difference from baseline in gait speed will have a standard deviation between 0.2 and 0.3 m/Sec.

Assuming that at Week 24 gait speed (change from baseline) difference between bimagrumab and placebo will be 0.15 m/sec and common SD = 0.25 m/sec, then sample size of 70 per group will give a power of 94% using a two-sided test at alpha level = 0.05 (based on testing strategy). The assumed standard deviation of 0.25 is the best available estimate given the literature review.

Short physical performance battery (SPPB)

The other secondary objective is to demonstrate that bimagrumab induces increases in SPPB (change from baseline) compared to placebo at Week 24. [Perera et al \(2006\)](#) estimated that, the meaningful change using effect size analysis, SPPB score changes corresponding to small and moderate effect sizes were 0.54 and 1.34 points respectively. Hence a meaningful difference in SPPB (change from baseline) increase has been identified as being 1.0 point over placebo.

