
 • Use of Mobility Aids Prior to Hip Fracture (3 months): 
 ○ Yes. ○ No (none). 
Use of Mobility Aids Prior to Hip Fracture (3 months) classified as recorded in the Baseline physical activity eCRF: “Within the last three months prior to hip fracture, what type of assisting device (referred to as mobility aid in this document) did the patient need for his/her daily activity?” If a mobility aid is recorded in the eCRF then the Use of Mobility Aids Prior to Hip Fracture (3 months) is considered as “Yes”, otherwise “No (none)”.
	
 • Primary and secondary efficacy. • Falls during the study.  . 	Secondary efficacy.

Subgroup	By-group Presentations	Covariates

 • 25OH Vitamin D at Screening: 
 ○ < 30 nmol/L (< 12 ng/mL). ○ ≥ 30 nmol/L (≥ 12 ng/mL). 	
 • Primary and secondary efficacy. • Falls during the study. • [REDACTED] 	

 • Amendment: 
 ○ Pre-amendment 2. ○ Post-amendment 2. 	
 • Primary and secondary efficacy. • Study drug administration. 	

[REDACTED]. DXA: Dual energy X-ray absorptiometry. eCRF: Electronic case report form. [REDACTED]. LBM: Lean body mass. SPPB: Short physical performance battery. SD: Standard deviation. Primary efficacy variable: Total LBM (kg). Secondary efficacy variables: Derived gait speed (m/sec) and total SPPB score. Subgroup presentation: First level of stratification will be “Overall” implying over all levels of stratification of the relevant planned subgroup presentation of the data.

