2.10.2.4 Sensitivity analysis (secondary)

[figure not shown]
Sensitivity analysis of change from Baseline in derived gait speed (m/sec) and total SPPB score will be analyzed in a similar manner as described for the primary efficacy variable in [Section 2.10.1.5](#) (Sensitivity analysis), without adjusting for multiplicity.

[figure not shown]
The sensitivity analysis will be performed for patients who are part of the SPPB/Gait speed Week 24 Completers FAS Analysis Subsets, respectively (as referenced in [Section 2.7](#) [Analysis Sets]).

[figure not shown]
Similarly, completers analysis will be repeated for the SPPB/Gait speed Week 48 Completers FAS Analysis Subset, respectively (see [Section 2.7](#) [Analysis Sets]).

[figure not shown]

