Derived gait speed (m/sec) will be assessed as part of the SPPB, over a 4 meter distance of a 6-meter course ([Peel et al \[2012\]](#)). It is the speed (m/sec) at which the 4-meter course is completed and is derived by dividing 4 meters (m) by the time (sec) to complete. Derived gait speed (m/sec) assesses a person's usual walking speed, which is defined as the speed a person normally walks from one place to another (for example, walking from one store to another). The patient will perform two recorded trials of walking across the defined course. The fastest time in seconds (to the nearest 0.01 sec) a patient takes to complete the assessment will need to be selected (the minimum of the two) and used to score the gait speed section of the SPPB eCRF. If only one walk was performed this time will be used. Any walking/mobility aid(s) used during the SPPB gait speed test performance will be captured in the eCRF. The scoring system is as follows:

- Time < 4.82 sec = 4 points.
- Time \geq 4.82 to \leq 6.20 sec = 3 points.
- Time \geq 6.21 to \leq 8.70 sec = 2 points.
- Time > 8.70 sec = 1 point.
- Patient is unable to do the walk = 0 points.

Chair stand

At first the chair stand test will be done one time (singular chair stand test). If the patient used arms to stand or the test could not be completed then the test procedure will be stopped and the score for the test is 0 points. If the patient stood up without using arms the aim of the second part of the test is to stand up five times (repeated chair stand test). The scoring system is as follows:

- Time to complete 5 stands \leq 11.19 sec = 4 points.
- Time to complete 5 stands \geq 11.20 to \leq 13.69 sec = 3 points.
- Time to complete 5 stands \geq 13.70 to \leq 16.69 sec = 2 points.
- Time to complete 5 stands \geq 16.70 to \leq 60 sec = 1 point.
- Patient is unable to complete 5 chair stands or has completed stands in > 60 sec = 0 points.

The total SPPB score will be calculated as the sum of the total standing balance score, gait speed score and chair stand score provided all three component scores are available.

Baseline data of the total SPPB score with the corresponding scores of the three individual component tests: Total standing balance, gait speed, and chair stand will be tabulated in a frequency table. Categories for each of the individual component tests will be:

- 0 points.
- 1 point.
- 2 points.
- 3 points.
- 4 points.

[figure not shown]
Categories for the total SPPB score will be:

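### The gait-speed and SPPB models adjust for walking-aid use before the fracture but not for the aid used in the Day 1 test, and no visible output shows how test-aid use changes by arm

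*SAP*

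**What the plan says.** Protocol 6.4.3 prefers an unaided walk but leaves room for an aid: "The patient should ideally complete the test without walking aids, unless he/she feels unsafe about completing the test without balance support". All types except wheeled walkers and rollators "can be used during the treatment period (from Day 1 to EOS"). The section does not say whether the aid must be the same from visit to visit, and it refers to the Study manual for test details.

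Both documents have the aid recorded. Protocol 6.4.3: "SPPB gait speed test performance will be captured in the eCRF including any potential usage of walking aids". SAP Appendix 1: "Any walking/mobility aid(s) used during the SPPB gait speed test performance will be captured in the eCRF". Appendix 1 derives gait speed as 4 m divided by the faster time, whether or not an aid was used. The same time gives the SPPB gait score.

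For gait speed and SPPB, SAP 2.10.2.3 fits a repeated-measures model in which "use of mobility aids prior to hip fracture (yes/no [none]) and Baseline value will be included as covariates", along with region, treatment date, fixation type and falls history, each with a visit interaction. SAP 2.6 shows that the aid covariate comes from a question about daily life: "Within the last three months prior to hip fracture, what type of assisting device". The aid subgroup in 2.6 is the same pre-fracture variable.

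The sensitivity analyses in SAP 2.10.2.4 follow those for lean body mass and use completer subsets: "The sensitivity analysis will be performed for patients who are part of the SPPB/Gait speed Week 24 Completers FAS Analysis Subsets". Neither these nor the deviation rules in 3.10 use the aid recorded at the test.

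**The concern.** Baseline gait speed is measured after surgery, with randomisation as late as Day 42. A patient who needed no aid before the fracture may well need one at Day 1, so the pre-fracture covariate does not describe the condition under which baseline was measured. The Day 1 test condition is closer to the outcome, is already collected and may predict recovery, yet it is not in the model.

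The aid may also change between Day 1 and Week 24. The trigger for using one is feeling unsafe, which a drug meant to improve strength and mobility could plausibly alter. If aid changes differ by arm, part of the measured difference in speed reflects how the test was walked.

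Gait speed supplies the first two inferences of the fixed sequence, so a failure there stops formal testing of SPPB and falls. Without a table of test-aid use, a reader could not judge how far either explanation applies.

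**Working it through.** **1. The plan's own figure.** Protocol 9.7 assumes that the "difference between bimagrumab and placebo will be 0.15 m/sec and common SD = 0.25 m/sec", with 70 per group and two-sided alpha 0.05, and states 94% power. The noncentrality is 0.15 / (0.25 × √(2/70)) = 3.55. Power is 94.1% by noncentral t (138 df) and 94.4% by normal approximation. The stated figure reproduces.

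**2. Precision lost by omitting the Day 1 condition.** The documents give neither the share aided at Day 1 nor the difference in recovery by aid status. Assumed: share p = 0.5, SD 0.25, and a gap d in mean change after adjustment for baseline speed.

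Share of variance = p(1−p)d² / SD² = 0.25 × d² / 0.0625. Sample-size equivalent = 1 / (1 − share).

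| d (m/sec) | Share of variance | Equivalent n ratio |
|---|---|---|
| 0.05 | 1% | 1.01 |
| 0.10 | 4% | 1.04 |
| 0.20 | 16% | 1.19 |

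This is an order of magnitude only. The value p = 0.5 gives the largest p(1−p), and p(1−p) overstates the spread left in aid status once baseline speed is known. On the other side, 0.25 is the planning SD of change and may exceed the model residual.

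**3. Aid changes that differ by arm.** Let e be the effect on measured speed of walking without the aid, and q the excess in the share of active over placebo patients who give it up. The measured difference becomes 0.15 + e × q. Neither e nor q is in the documents, so both signs of e are shown. Cells give the measured difference (m/sec) and power with 70 per group and SD 0.25.

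| e (m/sec) | q = 10 points | q = 20 points | q = 30 points |
|---|---|---|---|
| −0.15 | 0.135; 88.7% | 0.120; 80.5% | 0.105; 69.4% |
| −0.10 | 0.140; 90.8% | 0.130; 86.3% | 0.120; 80.5% |
| −0.05 | 0.145; 92.6% | 0.140; 90.8% | 0.135; 88.7% |
| +0.05 | 0.155; 95.4% | 0.160; 96.4% | 0.165; 97.2% |
| +0.10 | 0.160; 96.4% | 0.170; 97.9% | 0.180; 98.8% |

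With a positive e and no true difference in walking ability, the chance of a nominally significant result would be 5.2% to 10.9% over the same values of q, instead of 5%. With q = 0 the measured difference stays at 0.15.

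**4. Is the Day 1 aid a valid covariate?** SAP 3.4 requires Day 1 assessments other than DXA before the first infusion, so the aid used in that test is a pre-treatment value. Aid use at later visits may be affected by treatment and should not enter the model.

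**The case against.** The strongest defence is that the endpoint is coherent as planned. Protocol 6.4.3 measures usual walking speed, with aids allowed for safety, and comparing that between randomised arms is a legitimate question. Randomisation balances Day 1 aid use in expectation. The model already contains baseline speed and its visit interaction; that speed was measured under the Day 1 condition and so carries part of the same information. At the low end of the assumed range the gain is 1% of variance, against planned power of 94%. For SPPB the walk feeds one of three components, and no size can be given. Finally, the Study manual is not supplied and parts of the SAP are redacted, so a consistency rule or an aid table may exist elsewhere.

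Most of this stands, and it limits the point. It does not remove it: the plan already treats aid use as prognostic and lets its effect vary by visit, but takes it from before the fracture when the Day 1 test condition is also on file.

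A reader might infer that the omission biases the treatment effect, or that a real benefit will be under-measured because treated patients give up their aids. The documents support neither. Omitting a baseline factor does not bias the randomised contrast. Differential switching is plausible but not shown, and nothing in the documents says that an unaided walk is slower, so an overstated effect is equally open.

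**Conclusion.** The point holds as a matter of precision and interpretability. In the visible text, aid use at the test can differ between visits, it is recorded, and no model, sensitivity analysis or subgroup uses it.

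The precision at stake is about 1% to 16% of variance, assuming half the patients aided at Day 1, SD 0.25 and a gap of 0.05 to 0.2 m/sec after adjustment for baseline speed. The upper end rests on favourable, unsupported inputs.

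A shift in the contrast needs aid changes that differ by arm. Under the values assumed above, the measured difference would run from 0.105 to 0.18 m/sec around the planned 0.15; the documents fix neither size nor sign. A Day 1 covariate would not correct such a shift. Only a tabulation of aid use would reveal whether the condition for it is present.

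**What to change.** In SAP 2.10.2.3, add walking aid used in the Day 1 gait speed test (yes/no) and its interaction with visit to the gait-speed and SPPB models, in addition to pre-fracture aid use. Take it from the test that supplies the baseline value. Update the LSMEANS settings in SAP 3.11.1 to match.

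Add one table of test-aid use by visit and arm, with the Day 1 to Week 24 shift in both directions (aided to unaided, and the reverse).

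Any analysis restricted to patients with the same aid status at both visits should be labelled exploratory. It is selected after randomisation and drops the patients who gave up the aid.

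The data are already in the eCRF. The cost is SAP wording fixed before unblinding, one table, and the extra parameters: with one per scheduled post-baseline SPPB visit in Protocol Table 6-1, six through Week 24 and eight through Week 48.

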2.10.2.4 Sensitivity analysis (secondary)

[figure not shown]
Sensitivity analysis of change from Baseline in derived gait speed (m/sec) and total SPPB score will be analyzed in a similar manner as described for the primary efficacy variable in [Section 2.10.1.5](#) (Sensitivity analysis), without adjusting for multiplicity.

[figure not shown]
The sensitivity analysis will be performed for patients who are part of the SPPB/Gait speed Week 24 Completers FAS Analysis Subsets, respectively (as referenced in [Section 2.7](#) [Analysis Sets]).

[figure not shown]
Similarly, completers analysis will be repeated for the SPPB/Gait speed Week 48 Completers FAS Analysis Subset, respectively (see [Section 2.7](#) [Analysis Sets]).

[figure not shown]
2.10.2.5 Supportive analyses (secondary)

[figure not shown]
For all patients assigned to FAS, dose-response modeling will be performed for both derived gait speed (m/sec) and total SPPB score using the MCP-Mod approach as described in [Section 2.10.1.6](#) (Supportive analysis).

[figure not shown]

[figure not shown]

[figure not shown]

[figure not shown]

2.11 Safety evaluation

All safety analyses will primarily be performed on the SAF analysis set and will be presented by treatment group and across all four treatment groups combined (“Total”) unless otherwise specified. All safety assessments will be analyzed through to Week 48 (EOS). Descriptive statistics (see [Section 3.2](#) [Precision and summary statistics]) will be used to describe the safety variables.

2.11.1 General adverse events

Adverse events will be categorized based on date of onset or worsening relative to the first and last infusion of study drug as:

- Pre-treatment: Date of onset or worsening of the AE is prior to the start of first infusion of study drug.
- Treatment-emergent: Date of onset or worsening of the AE is on or after the start of the first infusion of study drug until the last infusion of study drug (expected per protocol at Week 20) + 56 days (see [Section 2.3](#) [Treatment pooling and data handling of pre-amendment 2] for more details).
- Post-treatment: Date of onset or worsening of the AE is after the date of last infusion of study drug (expected per protocol at Week 20) + 56 days.

Missing or incomplete AE onset dates will be imputed prior to categorization; algorithms for date imputations will be provided in RAP Module 8 (Programming Specifications). No imputation will be applied to AE end dates. Hence, if the end date is missing, the duration of the AE will be “continuing”.

All AEs reported will be listed. With the exception of the overview presentations, primarily only TEAEs/Post-treatment AEs will be summarized for each treatment group and across active bimagrumab treatment groups combined (“Active Total: Safety” - Includes bimagrumab 700 mg, bimagrumab 210 mg and bimagrumab 70 mg), overall and by region (Japan/Non-Japan) (see [Section 2.6](#) [Subgroups]). Percentages (%) will be derived relative to the number of patients “at risk” (in SAF analysis set or ongoing at the start of follow-up). At the time of the primary analysis number of patients “at risk” comprises:

- Incidence of AEs at Screening: All enrolled patients implying all patients who provided informed consent.
- Incidence of AEs in treatment: Patients assigned to the SAF analysis set regardless of study status, implying all patients entering the 24-week treatment epoch.
- Incidence of AEs in post-treatment follow-up:
 - Patients who completed treatment but are ongoing in post-treatment follow-up or who have discontinued during post-treatment follow-up.
 - Patients who prematurely discontinue treatment within the defined 24-week treatment epoch and who then continue study participation as part of the planned 4-week post-treatment follow-up.
 - Patients who completed treatment and post-treatment follow-up (study completed at the time of the primary analysis).

The same convention in view of patients entering post-treatment follow-up will apply at the time of the final update analysis.

In addition to the aforementioned, all AEs will be allocated to a time interval based on the date/relative study day of onset or worsening of the AE. The denominator for each time interval will again be the number of patients who are ongoing in the study at the first day of each time interval (i.e. patients “at risk” of experiencing an AE in the given interval provided that they have entered that time interval).

The time intervals are as follows:

- Day 1 to Day 30.
- Day 31 to Day 90.
- Day 91 to Day 180.
- Day 181 to Day 270.
- Day 271 to EOS (Target Day 336).

Adverse events data will be listed by treatment group, country, patient, and by start date/relative study day of onset or worsening of the AEs such that the AEs sort chronologically within a patient. The type of AEs that will be presented are:

- General and dictionary coding.
- Deaths
- SAEs.
- Adverse events leading to discontinuation of study drug.
- Adverse events of special interest.

Duration of event (days) will be calculated for those events not indicated as ongoing:

Duration (days) = (End date of event – Start date of event) + 1 day.

The latest MedDRA dictionary version will be used for coding and will be described in a footnote.

2.11.2 Overview of treatment-emergent adverse events (TEAEs), treatment-emergent serious adverse events (TESAEs) and post-treatment adverse events

Overview of AEs (TEAEs/Post-treatment AEs) and SAEs (TESAEs/Post-treatment SAEs) will be presented for:

- AEs.
- Deaths.
- Severe AEs.
- AEs leading to discontinuation of the study drug.
- AEs suspected to be related to the study drug.
- SAEs.
- Severe SAEs.
- SAEs leading to discontinuation of the study drug.
- SAEs suspected to be related to the study drug.

The number (n) and percentage (%) of patients with at least one of the aforementioned AEs/SAEs in each overview category will be presented. If a patient reported more than one adverse event within each of the aforementioned categories the patient will be counted only once in each overview category. The number of events (E) of the aforementioned AEs/SAEs in each overview category will also be presented.

The aforementioned overview of AEs (TEAEs/Post-treatment AEs) and SAEs (TESAEs/Post-treatment SAEs) will be summarized in separate tables by treatment-emergent/post-treatment, by treatment group and “Active Total: Safety”, overall and by region (Japan/Non-Japan) (see

[Section 2.6](#) [Subgroups]). Percentages (%) will be derived relative to the number of patients “at risk” (for treatment-emergent the patients in SAF analysis and for post-treatment the patients ongoing at the start of follow-up).

